13.5 Statistical methods for primary and secondary outcomes

13.5.1 Statistical methods for primary outcome

13.5.1.1 Trial

The primary estimand is a treatment policy estimand. This means that intercurrent events are not taken into account when the analysis is performed. This is similar to how an intention to treat analysis would be carried out. The specification of the estimand is below.

The electronic version of this document is the latest version. It is responsibility of the individual to ensure that any paper material is the current version. Printed material is uncontrolled documentation.

- **Population** – CYP with gender dysphoria who are in the CYPGS and are determined to be clinically eligible for GnRHa treatment and meet the eligibility criteria for the trial.
- **Endpoint** – The endpoint is 24-months post randomisation into the trial.
- **Treatment condition** – Treatment is GnRHa, either immediately or delayed for a year. The delayed treatment is the control treatment, and the treatment arm is the immediate arm.
- **Intercurrent event** – Intercurrent events are as below:
 - Failure to adhere to randomised treatment protocol – Non-compliance with the prescribed treatment regimen, including missed doses or incorrect administration
 - Premature discontinuation of the randomised treatment – Participants stopping the treatment before the study endpoint for any reason.
 - Death of participant during the trial period
 - Long-term physical or mental health hospital admission – Hospital admissions for physical health reasons that extend beyond a short-term stay and could impact the study outcomes
 - Serious adverse events that significantly impact the participant's health and require medical intervention (such as a severe allergic reaction)
 - Substance abuse: Development of substance abuse issues during the trial period
 - Pregnancy
 - Major changes in lifestyle or environment that could impact the participant's health or adherence to the trial protocol, such as relocation
- **Population level summary** – The population level summary will be the difference between the two arms at 24-months, as measured by the mean of the posterior, with the 95% credible interval.

The analysis of the primary outcome will be carried out using the Bayesian framework. Using the Bayesian framework means that the analysis will have to specify priors and allows for the analysis to give credible intervals, as opposed to confidence intervals, that are much easier to interpret.

The primary analysis model will be a Bayesian linear mixed model. The baseline score for the primary outcome will be included as a fixed effect, alongside the stratifying factors of site, birth registered sex, tanner stage and diagnosis of a neurodevelopmental disorder or trait. Random effects for participant will be included to account for clustering of longitudinal data within participants.

As this will be carried out using the Bayesian framework, priors used for all parameters estimated will be uninformative, flat priors. Derivation of the single primary outcome is detailed fully in the PATHWAYS TRIAL Statistical Analysis Plan.

13.5.1.2 HORIZON INTENSIVE

The primary outcome for HORIZON INTENSIVE is the KIDSCREEN-10. Analysis will be carried out in the same fashion as the Horizon trial, using a Bayesian linear mixed model within a Bayesian framework. Stratifying factors will be used as fixed effects and participant will be used as a random effect to allow for the clustered nature of repeated measures data. Priors will be uninformative. As the HORIZON INTENSIVE cohort is loosely matched to trial participants, this matching will be taken into consideration.

13.5.1.3 CONNECT

To assess whether the effect of GnRHa acts over and above the effect of age on the brain during puberty, mapping and comparison of brain structure, functional and metabolite trajectories in each study arm will be performed to establish effects of the treatment group. The model will include age, Tanner stage and birth-registered sex.

The approach will be to either restrict a-priori defined variables for confirmatory hypothesis testing or full reporting of all comparisons for exploratory research. GnRHa/no-GnRHa comparisons of brain imaging data will be made to establish mean group differences in individuals matched as far as possible for age and sex-registered at birth. This will be performed using linear mixed effect models, with subject as the random effect, and age, Tanner stage at time one and GnRHa treatment status (yes/no) as fixed effects. In secondary exploratory analysis, incorporated in the design matrices will be continuous variables such as change in cognitive function measures to examine outcome prediction pathways respectively.

13.5.2 Statistical methods for secondary outcome

13.5.2.1 *Continuous outcomes*

13.5.2.1.1 Trial

Continuous secondary outcomes will be analysed using the same estimand using the treatment policy intercurrent event handling method. The same method of analysis will also be used, maintaining the same fixed and random effect structure as the primary outcome analysis. Uninformative priors will also be used for parameters that are to be estimated.

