3.2.1.2 Clinical Inclusion Criteria

1. The child or young person meets diagnostic criteria for gender incongruence according to ICD-11. This diagnosis should be made or confirmed within the CYPGS. Specifically:
 - a. The CYP has a strong desire to be a different gender than the assigned sex;
 - b. The CYP has a strong dislike of sexual anatomy or anticipated secondary sex characteristics;
 - c. The incongruence must have persisted for a minimum of 2 years;
 - d. The CYP has a strong desire to 'transition', to live and be accepted as a person of the experienced gender.
2. The CYP wants puberty suppression for their gender incongruence and this care preference persists after receiving other care deemed appropriate from the CYPGS and other sources prior to the initiation of GnRHa.
3. The CYP is confirmed by the CYPGS to be in Tanner stage 2-5.
4. The CYP is younger than 15 years and 11 months at the time of consent to the trial.
5. The clinician in the CYPGS leading on care for that CYP considers that GnRHa for puberty suppression offers a reasonable prospect of benefit. This benefit might be achieved in relation to quality-of-life parameters (e.g., confidence in peer and family relations, participation in school and/or leisure activities, improved sense of well-being), mental or physical health.
6. The clinician in the CYPGS leading on care for an individual patient considers they have participated sufficiently for their holistic health and well-being in other forms of care for puberty suppression to be considered, in line with NMDT recommendations and this participation is reviewed by the NMDT.
7. The CYP has demonstrated sufficient understanding of the possible advantages and disadvantages of the proposed treatment including immediate psychological and physical impacts and also long-term implications, benefits and harms in the context of their personal situation and needs. Having considered this information, the child or young person has indicated that they wish to proceed with the treatment (assented).
 - a. To achieve this, this will involve serial discussions with clinicians, including those with specialist knowledge of endocrine interventions (e.g., paediatric endocrinologist, clinical nurse specialist, paediatrician with specialist knowledge).

The electronic version of this document is the latest version. It is responsibility of the individual to ensure that any paper material is the current version. Printed material is uncontrolled documentation.

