4.10.4 Demographics

Relevant demographic information will be collected prior to randomisation including initials, age (date of birth), birth-assigned sex, gender identity, country of birth, and ethnicity. Only initials, date of birth and ethnicity will be entered into the TRIAL and HORIZON INTENSIVE database.

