4.14.7 Bone Age X-Ray

Bone age X-Rays of the left hand/wrist will be performed at screening for all TRIAL participants. Bone age X-Rays will be reported using the Tanner Whitehouse II method. For TRIAL participants the month 12 and 24 scans are optional - bone age X-Rays do not need to be repeated if growth plates are fused. An initial bone age assessment will allow calculation of expected final height and comparison to actual final height can be made. For HORIZON INTENSIVE participants, bone age X-Rays will be performed at baseline only.

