6.1 Randomisation method

The method of allocation sequence is minimisation.

Participants will be randomized individually in a 1:1 ratio to immediate vs. delayed start of GnRHa. Participants will be minimised based on four stratifying factors. These are birth registered sex (Male/Female), Tanner stage at entry (stage 2/3, stage 4/5), a diagnosis of a neurodevelopmental disorder or high levels of traits (yes/no) and site (7 levels). There will be an initial burn in of 10 participants who are simply randomised to provide an initial imbalance, where the minimisation can then work from. This means the initial participants are allocated to arms, irrespective of their stratifying factors.

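### The model fixed for height in cm leaves out age and screening bone age, both collected before treatment; the comparison stays unbiased but gives up precision (about 6–14% of the 24-month SE on assumed growth curves)

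*Protocol*

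**What the plan says.** Section 13.5.1.1 gives the fixed effects used for KIDSCREEN-10: "The baseline score for the primary outcome will be included as a fixed effect, alongside the stratifying factors of site, birth registered sex, tanner stage". Neurodevelopmental diagnosis or trait completes the list, with a random effect for participant. Section 6.1 shows that the maturity stratifier has two levels: "Tanner stage at entry (stage 2/3, stage 4/5"). Section 13.5.2.1.1 then binds every continuous secondary outcome in the trial to that set: "The same method of analysis will also be used, maintaining the same fixed and random effect structure as the primary outcome analysis".

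Section 13.1.6 lists height in cm as a continuous physical measure, so the rule covers it, and no section makes an exception.

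Two further maturity measures are held at entry. Section 4.10.4: "Relevant demographic information will be collected prior to randomisation including initials, age (date of birth"). Section 4.14.7: "Bone age X-Rays of the left hand/wrist will be performed at screening for all TRIAL participants". The same section states one purpose for the X-ray: "An initial bone age assessment will allow calculation of expected final height and comparison to actual final height can be made". Neither measure appears as a covariate in the trial models.

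The protocol allows for age elsewhere. The CONNECT model in 13.5.1.3 includes it, and bone density is reported as an age- and sex-standardised z score (4.14.6, 13.1.6).

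**The concern.** A covariate set chosen for a quality-of-life T-score suits height less well. Eligibility covers Tanner 2 to 5 with an upper age limit only: "The CYP is younger than 15 years and 11 months at the time of consent to the trial". Over 24 months some participants have much growth left and others almost none. Baseline height separates them poorly, because a tall child early in puberty and a short one near adult height can measure the same. A two-level Tanner factor recovers only part of the difference. Bone age bears directly on remaining growth, which is why section 4.14.7 uses it to project final height.

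At stake is the width of the credible interval for an effect that section 2.2 names among those that may accumulate with puberty suppression, although it calls those analyses exploratory. Precision cannot easily be bought another way: section 13.4.1 says eligibility cannot be widened nor sites added, and it considers a trial of only 150.

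**Working it through.** **Plan's own figure.** There is none for height. The 91% power in section 13.4.1 concerns KIDSCREEN-10 and does not enter here.

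**Inputs from the protocol.** N = 226, allocated 1:1 (113 per arm); planned covariates as above, reading the baseline score as the baseline value of the outcome analysed.

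**Assumed inputs.** The protocol gives no growth SD. Height was simulated with 200,000 participants per scenario on assumed growth curves, with slower growth on treatment and the delayed arm starting at one year. Three quantities varied: SD of bone age around chronological age 0.7–1.3 years, measurement noise 0.5–1.0 cm, and 50–70% birth-registered female. Each scenario compared the residual variance of a single-visit ANCOVA (arm, baseline height, sex, two-level Tanner stage, neurodevelopmental indicator; site omitted) with that of the same model plus linear age and bone age.

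**Formulae.** If the added covariates remove a share R² of the residual variance:
- SE ratio = √(1 − R²)
- equivalent N = 226 / (1 − R²)

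**Results for age plus bone age.**

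| Visit | R² | SE ratio | SE reduction | Equivalent N |
|---|---|---|---|---|
| 12 months | 0.08 to 0.21 | √0.92 = 0.96 to √0.79 = 0.89 | 4–11% | 246 to 286 |
| 24 months | 0.11 to 0.26 | √0.89 = 0.94 to √0.74 = 0.86 | 6–14% | 253 to 305 |

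At 24 months, 253/226 = 1.12 and 305/226 = 1.35, that is 12–35% more participants. With 150 recruited, 150/0.89 = 169 and 150/0.74 = 203.

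**In centimetres, with complete follow-up.** SE = residual SD × √(2/113) = residual SD × 0.133; the 95% half-width is 1.96 times that.
- Largest gain: residual SD 2.54 falls to 2.19 cm, half-width 0.66 falls to 0.57 cm.
- Smallest gain: residual SD 2.79 falls to 2.64 cm, half-width 0.73 falls to 0.69 cm.

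**Which covariate matters.** At 24 months the variance ratio is 0.80–0.95 with age alone (SE 3–11% lower) and 0.75–0.90 with bone age alone (SE 5–13% lower). Bone age carries most of the gain.

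**Cost in degrees of freedom.** The planned model uses 12 (intercept, arm, baseline, sex, Tanner, neurodevelopmental status, six site contrasts), leaving 226 − 12 = 214. Two added terms inflate the SE by √(214/212) = 1.005, about 0.5%. With two sex interactions as well, √(214/210) = 1.009, about 0.9%. The interactions were not in the simulated gain.

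**Sensitivity to the curves.** A separate simulation with different assumed curves and bone-age error SD 0.5–1.0 years also gave SE ratios of 0.86–0.94 at 24 months.

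**The case against.** The strongest reply is that nothing here is invalid. Allocation is minimised on sex, Tanner group, neurodevelopmental status and site, and all four are in the model with the baseline value. Adjusting for baseline and minimisation factors is conventional. That stands: the loss is one of efficiency, and a reader who inferred bias in the height contrast would be wrong.

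A second reply is that outcome-specific covariates commonly wait for the statistical analysis plan. That would hold if the protocol were silent. But section 13.5.2.1.1 states the structure outright, whereas 13.5.1.1 defers the derivation of the primary outcome and 13.8 defers subgroup detail. An analysis plan that added growth covariates would depart from the protocol.

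Four stronger readings are tempting, and the documents do not support them.
- *The same loss affects weight, BMI and blood pressure.* Only height was computed, and the protocol gives no variance or prognostic figure for the others. Blood pressure is not a growth outcome. BMI is collected as a centile (4.14.5), while 13.1.6 does not name its scale.
- *The gain is larger.* Some assumed growth-spurt curves give SE ratios down to 0.78. Nothing in the protocol favours those curves, and the two simulations reported above agree on 0.86–0.94.
- *The month-24 window of ±8 weeks adds serious noise.* A uniform window has SD 16/√12 = 4.6 weeks, or 0.09 years. At an assumed 2–6 cm per year this is 0.18–0.53 cm. Against residual SDs of 2.80 and 2.54 cm, it is 0.18²/2.80² = 0.4% to 0.53²/2.54² = 4.4% of variance, about 0.2–2% of SE.
- *The bone age X-ray has no planned use.* Section 4.14.7 gives it one, in projecting final height. It is only absent from the models.

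**Conclusion.** The point holds for height, as an avoidable loss of precision and not as an error of validity. Adding age and bone age would lower the 24-month SE by about 6–14%, worth roughly 12–35% more participants, against under 1% of SE in degrees of freedom. The direction does not depend on the particular curves tried; the size does, because the documents supply no growth data. It also rests on a single-visit ANCOVA standing in for the mixed model, and on baseline height being in that model. Extension to weight is plausible but unquantified. BMI and blood pressure are outside the point.

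**What to change.** In section 13.5.2.1.1, add an exception for height. The model keeps the baseline value of the outcome and all stratifiers, and adds prespecified fixed effects for age at randomisation and screening bone age, each with an interaction by birth-registered sex. Report age- and sex-standardised height beside raw cm. Weight may be treated likewise if the team judges it worthwhile.

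Use age at randomisation, not age at assessment. The latter contains visit timing after randomisation, which could differ between arms because their injection schedules differ (Appendix A, Tables 4 and 5).

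The cost is a sentence or two in the protocol, matched in the analysis plan. No new measurement is needed; the team should confirm that the screening bone age reading is entered in the trial database.

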13.5.2.1.2 HORIZON INTENSIVE

Continuous secondary outcomes will follow the same analysis plan as the primary analysis.

13.5.2.2 *Binary outcomes*

13.5.2.2.1 TRIAL

Binary secondary outcomes will be analysed using the same approach as the primary analysis. The estimand will be the same as the primary analysis, utilising the treatment policy intercurrent event handling method. The analysis carried out shall use a logistic mixed model, still retaining the fixed and random effect structure of the The electronic version of this document is the latest version. It is responsibility of the individual to ensure that any paper material is the current version. Printed material is uncontrolled documentation.

primary analysis. Uninformative priors will be used for parameters that are to be estimated.

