2.1.1 Why not use a placebo-controlled, double-blind design?

It is not possible to blind GnRHa treatment for any significant period of time. Puberty suppression (or its absence) cannot be blinded for any significant period of time. While the onset and rate of puberty shows considerable inter-individual variation, the purpose of this intervention is to stop puberty during the time period when its effects would be most obvious, during the development of secondary sex characteristics. Hence any advancement of puberty would be obvious to the young person, thus unblinding them to treatment allocation. For post-menarcheal females, puberty suppression stops periods, in both arms identifying treatment allocation. Treatment for puberty suppression typically lasts for several years, so no young person would remain blind.

In the absence of blinding for any period of time, is there benefit to using a placebo? For all bar post-menarcheal females, it is possible young people would be blinded to treatment for several months, so that initial measured outcomes might be masked to treatment arm. This would be an important consideration if very short-term effects were of particular interest, although this would need to be balanced against inconvenience for patients in attending hospital for sham injections. It would be unclear when and whether to stop sham injections as unblinding would likely occur at varying points for different patients.

Knowledge of the intervention is part of the effect. Finally, part of the potential benefit (to be studied) of GnRHa, is patients' knowledge that their puberty is being suppressed. The efficacy of GnRHa in suppressing puberty is not being assessed in this study, because this is well-documented as highly efficacious in this regard. The question is whether patients have better psychological outcomes, including higher quality of life, reduced mental health symptoms when they stop experiencing ongoing development of puberty. There are also important questions to be addressed about physical and cognitive effects in the short- and medium-term as well as longer-term benefits and risks.

Summary. For these reasons, blinding and placebo-control are not only unlikely to achieve their aims, but they would potentially miss possible short-term benefits of the intervention that need to be measured in providing a comprehensive picture of benefits and risks.

2.2 Choice of immediate vs delayed treatment arms.

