13.1.7 Binary Physical Outcomes

- a) Adverse events
- b) Puberty staging (Tanner staging, both clinical and self-reported)

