13.5.2.2.2 HORIZON INTENSIVE

Binary secondary outcomes will use the same fixed and random effects, and uninformative priors. Instead of a linear mixed model, a logistic mixed model will be used. Other outcomes not falling into these categories will reflect the analysis methods used in the trial.

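### Uninformative (flat) priors in the logistic models fail if a sparse binary secondary outcome leaves an arm or a site without events

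*Protocol*

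**What the plan says.** Protocol 13.5.1.1 states for the primary linear mixed model that "priors used for all parameters estimated will be uninformative, flat priors". The fixed effects are baseline score, site, birth-registered sex, Tanner stage and neurodevelopmental status, with a random effect for participant. The arm difference is to be reported "as measured by the mean of the posterior, with the 95% credible interval".

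Protocol 13.5.2.2.1 then says "Binary secondary outcomes will be analysed using the same approach as the primary analysis". It names a logistic mixed model with the same fixed and random effects, and adds "Uninformative priors will be used for parameters that are to be estimated". Section 13.5.2.2.2 repeats this for the non-randomised cohort: "Binary secondary outcomes will use the same fixed and random effects, and uninformative priors". No scale is given in either place, and neither section mentions empty cells.

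Section 13.12 plans alternative priors, but describes them as a check on the primary analysis. Section 6.1 gives site seven levels. The outcomes in 13.1.7 headed binary are adverse events and puberty staging; hospitalisations are listed in 13.1.3.

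**The concern.** A flat prior is workable in a linear model because the normal likelihood falls away in both directions. A logistic likelihood need not. If a group defined by a fixed effect has no events, the likelihood levels off at a positive constant as that group's coefficient goes to minus infinity. A flat prior then has nothing to close the integral. The joint posterior is improper, and the posterior mean and credible interval that the protocol asks for do not formally exist. Software would return a number anyway, fixed by its internal bounds.

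Reading the term as a very diffuse proper prior removes the impropriety but not the dependence. When an arm is empty, the prior's width and the choice of reference arm determine the mean, the far limit, and sometimes whether the interval excludes no difference. At stake is whether a published effect on a sparse secondary outcome reflects the data or a default setting.

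**Working it through.** **Inputs.** From the protocol: 226 participants allocated 1:1, so 113 per arm (13.4.1, 6.1); seven sites (6.1); uncommon paediatric reactions at 1 in 1000 to 1 in 100 (8.3). Assumed: equal sites of 226/7 ≈ 32; outcome risks of 5% and 10% for the site calculation; all event counts. The protocol gives no figure of its own for binary outcomes, so there is nothing to reproduce. The posteriors below come from grid integration of a simplified logistic model: one yes/no result per participant, with no site or participant effect.

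**1. Empty arm, flat prior cut at ±B.** For 0/113 (immediate) against 3/113 (delayed), the posterior for the log-odds ratio b is nearly uniform from -B up to about zero, so its mean is about -B/2:

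| B | posterior mean of b | 95% interval |
|---|---|---|
| 10 | -5.6 | -9.8 to -0.7 |
| 20 | -10.7 | -19.5 to -1.4 |
| 50 | -25.7 | -48.8 to -2.5 |

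The mean has no limit as B grows. All three intervals exclude zero, although Fisher's exact p is 0.25.

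**2. Empty arm, diffuse proper prior.** With Normal(0, 10) on intercept and arm, and arm coded 0/1:
- 0 v 2 gives an interval of -22.8 to -0.4, which excludes zero.
- 2 v 0 gives -0.15 to 14.9, which does not.

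These are the same data with the arms swapped, and Fisher's p is 0.50 for both. The asymmetry arises because the intercept prior constrains the reference arm's log-odds only.

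**3. How sparse must an outcome be?** P(at least one arm empty) = 1 - [1 - (1-p)^113]². At equal risk p in both arms:
- p = 1%: (0.99)^113 = 0.321, so 1 - 0.679² = 54%
- p = 2%: 19%
- p = 3%: 6%
- p = 5%: 0.6%

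An empty arm is therefore a concern only at about 3% risk or below. For 1 v 3 events the flat-prior interval is already stable (-4.8 to 0.9).

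**4. Empty site.** P(at least one of seven sites event-free) = 1 - [1 - (1-p)^32]^7:
- p = 5%: (0.95)^32 = 0.194, so 1 - 0.806^7 = 78%
- p = 10%: (0.90)^32 = 0.034, so 1 - 0.966^7 = 22%

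The joint posterior is improper in these cases too, but it is the site coefficient that runs away. The arm effect is still informed by the other sites, so the main practical symptom is failed convergence.

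**5. Puberty staging.** The protocol gives no binary cut for this outcome. Suppose it is stage 2/3 v 4/5, with entry stage in the model, 56 stage 2/3 and 57 stage 4/5 entrants per arm, and 0 v 15 stage 2/3 entrants progressing (all assumed). Mean of b under flat priors cut at ±10, ±20 and ±50:
- all stage 4/5 entrants stay 4/5: -3.5, -7.1, -17.2 (diverges)
- one delayed-arm stage 4/5 entrant later recorded as 2/3: -3.1, -3.5, -3.5 (stable)

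Divergence therefore needs two conditions together: no progression in the immediate arm, and no downward re-recording in the delayed arm.

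**The case against.** The strongest reply is that the protocol does not commit itself to an analysis that breaks. The binary sections say uninformative, not flat, so carrying the flat wording over is an inference from the phrase linking the two analyses. By the same phrase one could argue that the alternative-prior analysis carries over as well. Prior scales, binary cuts and the modelling of adverse events usually belong in the statistical analysis plan, which is not at hand. This stands in part, and it is why the point is minor. It does not dispose of it: the protocol has fixed the type of prior, and both natural readings of that type fail when an arm is empty.

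A reader might infer three stronger claims that the document does not support.

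- **That the effect on puberty staging will be undefined, because suppression is** "because this is well-documented as highly efficacious in this regard". At a 2/3 v 4/5 cut the immediate arm is not empty, since its stage 4/5 entrants count as events, and one discordant staging in the delayed arm removes the divergence. The chance that no stage 2/3 entrant progresses (57%, 32% and 6% with 56 staged, at individual progression of 1%, 2% and 5%) is not the chance of an undefined effect.
- **That the adverse-event analysis will fail.** The outcome is listed simply as adverse events. Section 8.1 lists many commonly reported effects, and both arms are treated by month 24, so any-event would not be empty. The empty-arm rates in step 3 reach adverse events only if single reactions are modelled separately, which the protocol does not state.
- **That safety oversight is compromised.** The data monitoring committee assesses adverse event data directly (14.3), and no stated decision rule uses these intervals.

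**Conclusion.** The concern holds in a limited form. As written, the prior rule for the logistic models yields an improper joint posterior, or one dominated by prior scale and arm coding, whenever a sparse outcome leaves an arm empty; an event-free site is enough to make the flat-prior joint posterior improper. Empty sites are the likelier event (78% at 5% risk, 22% at 10%, assuming equal sites), but their effect is mainly on the site coefficient and convergence. Empty arms matter only for uncommon outcomes, such as hospitalisation if analysed yes/no or a single reaction if modelled separately. Puberty staging is exposed only under the joint conditions in step 5. Common outcomes are unaffected.

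The mathematics of the empty cell is exact. How often it would arise depends on outcome definitions that the protocol does not give. The harm is confined to published secondary estimates. Severity: minor.

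**What to change.** In 13.5.2.2.1 and 13.5.2.2.2, replace the uninformative priors for the logistic models with proper weakly informative priors on the arm and covariate log-odds coefficients, for example Normal(0, 2.5). Code arm as -0.5/+0.5, centre the covariates, and give the intercept a wide proper prior, for example Normal(0, 10). Fix the scales in the statistical analysis plan before unblinded data are seen. Extend the alternative-prior analysis in 13.12 to binary outcomes, and show raw counts beside sparse estimates.

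With these priors, 0 v 3 gives -5.97 to 0.18 and 3 v 0 gives the mirror image, so the reference arm no longer matters. The scale still does: with a flat intercept, 0 v 3 has a mean of -0.93 under Normal(0, 1) and -2.56 under Normal(0, 2.5). That is why it must be set in advance and varied in sensitivity analysis.

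The cost is wording in three sections and slight shrinkage of very large odds ratios. Against a flat prior, the mean log-odds ratio moves from -1.35 to -1.31 for 10 v 30 events, from -1.61 to -1.54 for 5 v 20, and from -2.73 to -2.45 for 2 v 20.
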